
2. Objective

Analyzing CSF samples from different age groups to identify biomarkers that undergo significant changes during the aging process, such as amyloid-beta ($A\beta42$), tau protein (including its phosphorylated form, p-tau181), and other proteins related to neuroinflammation and blood-brain barrier function.

Establishing a predictive model through the analysis of CSF protein levels and classification across different age stages, to enable the early diagnosis of neurodegenerative diseases (e.g., Alzheimer's disease). This could allow for the detection of diseases before clinical symptoms appear, providing the possibility for early intervention and treatment.

Investigating the dynamic changes of CSF biomarkers at different stages of disease to understand their roles in disease progression, including changes in the early, middle, and late stages. This will help to better understand the pathological process and identify potential

therapeutic windows.

Creating a database of CSF biomarkers that encompasses different age groups, disease states, and treatment responses. This database will provide valuable data resources for future research, facilitating the scientific community's understanding of neurodegenerative diseases and the development of new therapies.

Through the achievement of these objectives, this study aims to advance the development of CSF biomarkers in neuroscience research and clinical applications, improving the diagnosis, management, and treatment of aging and neurodegenerative diseases.

3. Method

Prospective Collection of Cerebrospinal Fluid from Patients Aged 0-90 Years Without Neurological Diseases:

Study Duration: 1 year, starting from the date of ethical approval and ending 1 calendar year after the date of ethical approval.

Inclusion Criteria:

Patients aged 0-90 years.

Patients admitted for surgery under spinal anesthesia due to non-neurological conditions such as lower limb fractures, hemorrhoids, etc.

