Pediatric patients requiring surgery for tethered cord syndrome.

Exclusion Criteria: Patients with neurological diseases, including but not limited to encephalitis, Parkinson's disease, Alzheimer's disease, hydrocephalus, brain tumors, and psychiatric disorders.

Withdrawal Criteria: Participants may voluntarily withdraw from the study at any time for any reason.

Specific Research Protocol:

Data Collection: Clinical data will be collected, including the patient's name, gender, age, and primary diagnosis. This information will be sourced from the hospital admission case system.

Cerebrospinal Fluid (CSF) Collection:

During spinal anesthesia, CSF is withdrawn to confirm the correct placement in the subarachnoid space before administering the anesthetic, with approximately 1-2 mL of CSF retained.

During surgery for tethered cord syndrome, 2 mL of CSF is collected before opening the dura mater.

The collected CSF is placed in a 0°C insulated container for storage and transportation, then centrifuged in the laboratory and stored at -80°C until further analysis.

After the collection is complete, multi-omics analyses, including proteomics and metabolomics, will be conducted.

Proteomics Analysis:

Sample Preparation:

100 µL of CSF is mixed with high-abundance protein depletion resin to enhance proteome depth, incubated at room temperature for 20 minutes, and the eluate is collected.

The sample is concentrated using a 3k molecular weight cutoff protein concentrator at 12,000 g for 30 minutes and exchanged with lysis buffer (8M urea) for protein denaturation.

After centrifugation at 12,000 g, less than 50 µL of solution remains in the tube.

The concentrated sample is reduced with 10 mM tris(2-carboxyethyl)phosphine hydrochloride at 32°C for 40 minutes, followed by alkylation with 40 mM iodoacetamide at room temperature in the dark for 30 minutes.

CSF samples are digested in two steps using 2.5 $\,\mu g$ of endoproteinase and 2.5 $\,\mu g$ of trypsin for 12 hours.

The peptides are acidified with trifluoroacetic acid, desalted using a 2 mg liquid-phase ion exchange column, and the eluate is dried using a vacuum concentrator.

Each batch is labeled with 56 μg of TMT16plex reagent for peptides from each sample. After 1-hour incubation at room temperature, TMT labeling is quenched with

hydroxylamine, and 16 samples from a batch are pooled and fractionated using a C18 column.

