Fractions are separated into 96 fractions with a gradient from 5% to 35% acetonitrile in 10 mM ammonia water at a flow rate of 1 mL/min. The first to seventh, 37th, and 67th fractions are pooled, and the remaining fractions are evenly pooled and vacuum dried.

The dried peptide powder is reconstituted in 2% acetonitrile/0.1% formic acid and analyzed by LC-MS/MS.

Data Analysis:

MS raw data is searched against the human protein fasta file downloaded from UniProtKB14, which contains 20,394 protein entries.

The parent ion mass tolerance is set to 10 ppm, and the fragment ion mass tolerance is set to 0.02 Da.

Subsequent statistical analysis is performed by comparing the abundance ratios of samples within the same batch to the combined sample.

Bioinformatics software is used to analyze the mass spectrometry data, including protein identification, quantification, and differential analysis.

4. sample capacity

Participants will be divided into 9 groups based on age, with each group covering a 10-year range (1-10 years, 11-20 years, etc.), totaling 9 groups. Each group will include 10-15 participants, with a planned total enrollment of 100-150 cases.

5. Data management and confidentiality

Data Entry and Modification:

Data entry and management will be handled by [name] and [name]. To ensure accuracy, two data administrators will independently enter and cross-check the data.

Database Locking:

Once the database has been confirmed to be accurate, it will be locked by the principal investigator and statistical analysts. All records related to participant identities will be kept confidential and will not be disclosed outside the scope allowed by relevant laws and/or First edition 2024-06-27

regulations.

6. informed consent

Before the clinical study begins, the researchers must provide detailed information to the participants or their legal guardians, including the nature of the study, its purpose, potential benefits, and risks. This ensures that participants or their legal guardians fully understand the clinical study. The clinical study can only commence after the informed consent form has been signed.

Each patient must provide detailed contact information, including their address and phone number. Additionally, the researcher will sign the informed consent form with the patient before the surgery and provide the patient with their contact information so that the patient can reach the researcher at any time.

7. Adverse Event Reporting

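### Nine age groups of 10-15 participants give a total of 90-135, not the planned 100-150

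*Protocol*

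**What the plan says.** Section 4 of the Protocol (sample capacity) fixes three quantities in two consecutive sentences. The first gives the number of groups: "Participants will be divided into 9 groups based on age, with each group covering a 10-year range", repeated at the end of the same sentence as "totaling 9 groups". The second gives the group size and the total: "Each group will include 10-15 participants, with a planned total enrollment of 100-150 cases".

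Three other places bear on these figures, all in section 3 (Method):

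- **Age range.** The heading reads "Prospective Collection of Cerebrospinal Fluid from Patients Aged 0-90 Years Without Neurological Diseases", and the inclusion criteria repeat the 0-90 range.
- **Withdrawal.** "Participants may voluntarily withdraw from the study at any time for any reason". No rate is attached, and no allowance for loss or unusable samples is linked to the total.
- **Duration.** The study runs for one year, "ending 1 calendar year after the date of ethical approval".

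**The concern.** The number of groups, the group size and the total are all fixed, and the third should be the product of the first two. It is not, at either end of the range. Because both ends are off, one mistyped digit does not explain the difference.

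What is at stake is the recruitment target. These are the only sample-size figures in the Protocol, and enrolment has to fit into one year. A team that meets every group minimum can still miss the stated total. A team aiming for the top of the stated range must either stop at 135 or put more than 15 people in some group. The total also sets the laboratory workload, because the proteomics section labels and pools samples in batches of 16.

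A smaller, separate ambiguity lies in the same sentence. Eligibility starts at age 0, but the bands are described as "each group covering a 10-year range (1-10 years, 11-20 years, etc.), totaling 9 groups". Read literally, an eligible infant under one year has no group.

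**Working it through.** **Inputs** (sections 3 and 4 of the Protocol): number of groups g = 9; participants per group 10 to 15; stated total 100 to 150; eligible ages 0-90 in ten-year bands; no stated rate of withdrawal or sample loss.

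**Step 1: try to reproduce the stated total.** Total = g × participants per group.

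| | Computed | Stated | Difference | Stated / computed |
|---|---|---|---|---|
| Low end | 9 × 10 = 90 | 100 | 10 | 100/90 = 1.11 |
| High end | 9 × 15 = 135 | 150 | 15 | 150/135 = 1.11 |

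Neither end is reproduced. On one common basis, the computed figure is 10% below the stated one at both ends (10/100 and 15/150).

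**Step 2: what the stated total implies per group.** 100/9 = 11.1, against a stated minimum of 10. 150/9 = 16.7, against a stated upper figure of 15. Since 9 × 16 = 144 < 150, a total of 150 forces at least one group to hold 17 or more. Since 9 × 15 = 135 < 136, every total from 136 to 150 forces at least one group to hold 16 or more.

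**Step 3: totals that satisfy both statements.** From max(90, 100) = 100 to min(135, 150) = 135. A consistent plan therefore exists, but only over 100-135.

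**Step 4: what could produce 100-150.** The equal ratio at both ends suggests a single cause. Two candidates fit exactly:

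- *Ten groups:* 10 × 10 = 100 and 10 × 15 = 150. This contradicts the number nine, stated twice, and the age span: 90 years / 10 years per band = 9 bands.
- *A 10% loss allowance,* N/(1 − d) with d = 0.10: 90/0.9 = 100 and 135/0.9 = 150. The rate is an assumption, since the Protocol gives none. At d = 0.05 the range would be 95-143, and at d = 0.15 it would be 106-159, so only a rate close to 10% fits.

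**Step 5: laboratory workload.** At 16 samples per batch, rounded up, 90-135 samples need 6-9 batches (90/16 = 5.6; 135/16 = 8.4) and 100-150 need 7-10 (100/16 = 6.3; 150/16 = 9.4). The ambiguity is worth about one batch at each end.

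**Step 6: the age label.** Continued literally, nine bands starting at 1-10 run to 81-90, while eligibility is 0-90. If age is counted in completed years, age 0 falls outside every band. If the labels mean year of life (first to tenth, and so on), nine bands cover exactly the 90 years from birth and only the label is loose. The text does not say which is meant.

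**The case against.** The strongest reply is that this is a loosely rounded recruitment range in a one-time sampling study with no treatment allocation. No power calculation or test is tied to the total. At the low end there is strictly no conflict, because at least 10 per group and at least 100 overall can both hold, for example with 11 or 12 per group. At the high end, the 10-15 may be a planning range rather than a rule that closes a full group. The age bands are given only as an illustration and can be read to cover the whole span.

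Much of this limits the size of the point. It is true that 100-135 works, that no power claim is affected, and that the low end is a failed derivation rather than two instructions that cannot both be met. It is also fair that a ten-group slip explains the figure as well as a loss allowance does, and the sponsor should consider both.

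The reply does not remove the point. The text says each group will include 10-15, which sets an upper figure of 15, and totals of 136-150 lie within the planned range while exceeding it. Nor can a reader choose between the two explanations: one would change the number of groups, while the other keeps nine and makes 10-15 the number evaluable. On the age label, the objection largely succeeds: it is a request for clarification and would not stand as a finding by itself.

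**Conclusion.** The concern holds. As written, the Protocol's only sample-size figures disagree: nine groups of 10-15 give 90-135, and the plan says 100-150. The gap is 10 participants at the low end and 15 at the high end, 10% of the stated figure in each case. Totals of 136-150 cannot be reached without exceeding 15 in some group; totals of 100-135 are workable.

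This rests only on the numbers printed in section 4 and on multiplication. It does not depend on which explanation for the discrepancy is right. The consequence is an unclear enrolment target, not lost power. It should be fixed because the error is plain and the correction nearly free. Confidence is high for the total. The point about the first age band is conditional on how age is counted and is secondary.

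**What to change.** In section 4, make the three figures agree. Either:

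- restate the planned total as 90-135, for nine groups of 10-15; or
- keep 100-150 and state the basis that yields it, for example a 10% allowance for withdrawals and unusable samples, with 10-15 defined as evaluable participants per group.

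If ten groups were in fact intended, the group count needs correcting instead, together with the age bands and their fit to the 0-90 eligibility range.

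In the same edit, state that age is in completed years and label the bands so that every eligible age belongs to exactly one group. A first band of 0-10 would do this, but it spans eleven completed years, so the ten-year wording would need adjusting for it. Alternatively, align the eligible age range with the bands.

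The cost is one sentence for the total and one for the age label. Under either of the first two options the number of groups stays at nine, and no patients are needed beyond the range already planned.
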